
**B.3. Innovation:** There are six major RCTs on polypills currently on-going or planned, three of these RCTs-TIPS-3, HOPE-3, and HOPE-4, are primary prevention studies, two of them-PROPS and SECURE are secondary prevention trials and PolyIran study is aimed at both primary and secondary CVD prevention. The innovative aspects of the SMAART trial include: **First**, this will be to our knowledge the first study to evaluate the feasibility of a polypill on secondary risk reduction among stroke survivors in resource-limited SSA setting with the potential to generate results that will inform research agenda and policy on the utility of the polypill in other LMICs. **Second**, although SMAART is a phase 2 study, a medium to long-term follow-up of 48-weeks is planned to allow investigators to assess changes in the carotid intima-media thickness, a US Food and Drug Administration approved and validate surrogate marker of CVD risk as a primary outcome measure, and compositely assess the sustainability of adherence to the polypill in LMICs as well as collect preliminary data on blood pressure and lipid control and cardiovascular events. Finally, even if SMAART were not to meet its primary endpoint, we will collect substantive data on feasibility, tolerability, adherence, risk factor control estimates, quality of life, and functionality, which could inform the design and conduct of future studies of the polypill strategy for high vascular risk individuals in SSA.

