**D.4.7.3. Follow-up and Outcome Evaluations:** Participants will be followed for 12 months with scheduled visits at months 1, 3, 6, 9 and 12 for clinical assessments and primary, secondary and tertiary/feasibility study outcome evaluations as shown in **Table 1**.

**D.4.7.4. Management of Possible Treatment related side effects:** Participants who experience side-effects will be reviewed by their physicians to assess severity and appropriate measures instituted.

**D.4.7.5. CIMT Assessment:** Primary endpoint will be CIMT burden. Each study participant will undergo Carotid Doppler ultrasonic evaluation at baseline and month 12 for evidence of clinical or sub-clinical carotid artery disease- a validated surrogate marker of atherosclerosis. To achieve reliable ultrasonic measurements of the common carotid artery IMT a standardized protocol and strict quality control procedures will be followed by two local experienced sonographers who will be blinded to the participants group status and risk factor levels to ensure we achieve unbiased results. CIMT will be measured at 1 cm portions of the distal left and right common carotid artery far walls with a linear transducer (transducer frequency of 7.5 MHz) with axial resolution of 0.10mm, and calculated automatically over 3 cardiac cycles following the Mannheim consensus. Average thickness of left and right carotid arteries will be used as outcome measure. We have experience in measuring CIMT as a primary outcome in our EVERLAST study (NTW010479).

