#### D.4.8. Outcome measures:

**Table 1.** Definitions of Primary & Secondary Outcome Measures to be assessed in SMAART Trial.

Variable	Brief Description
Carotid Intimal Media Thickness Primary Outcome Measure	End of study CIMT value will be subtracted from baseline CIMT value & divided by length of follow-up & the rate of change in CIMT (mm/yr) between treatment arms & change in intima-media (artery wall) thickness and extent of atherosclerotic plaques in the carotid artery bifurcation measured.
Change in Adherence to therapy Secondary outcome measure	This will be measured at baseline and at month 12 clinic visits using the self-reported Morisky-Green questionnaire(MAQ)  and pill count. Patients have to meet both criteria for adherence at the in-person visits to be considered adherent.
Safety & Tolerability Indicators Secondary outcome measure	Renal function: Serum creatinine measurements to calculate eGFR using the CKD-EPI  formula at baseline and months 1 and 12. Liver function: Elevations in liver enzymes will be assessed, if AST or ALT rises >5x Side effects profile: Adverse events will be closely monitored & side effects will be documented according to the NIH/NCI Common Toxicity Criteria  Discontinuation of medications: Reasons and clinical indications for stopping treatment in both arms will be compared in both arms. Regimen adjustments: Reasons for modifications in dosages including addition of new CVD agents, will be assessed in both treatment arms.
Health-related Quality of Life	The EQ-5D questionnaire  will be used to assess state of health of study subjects at baseline and Month 12.
Change in Patient Satisfaction	The treatment Satisfaction Questionnaire  for Medication will be administered at baseline and month 12.
Cognitive Dysfunction Indices	The Montreal Cognitive Assessment (MOCA) scale  will be used to assess global cognitive dysfunction at months 0 and 12.
Functional Status	Functional status after stroke will be assessed using the modified Rankin scale with a score from 0 to 6.
Depression	Depression will be assessed using the Beck Depression Inventory and Hamilton Rating Scale for Depression at months 0 and 12. 

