CVD Risk Factor Control Tertiary/feasibility	1. Blood pressure control will be defined as Systolic BP <140 mmHg and/or diastolic DP <90mmHg or (>135/85mmHg in diabetes patients). Mean change in SBP at month 12 from baseline will be compared in the two treatment groups. 2. Dyslipidemia: control will be defined by change in mean LDL-cholesterol <100mg/dl or <70mg/dl. Mean change in LDL-C at month 12 from baseline will be compared in the two treatment groups.
Incidence of Adverse events Tertiary/feasibility	1. Recurrent stroke: fatal/ severely disabling stroke or non-fatal stroke; Coronary Artery Disease: Acute STEMI/NSTE deaths 2. Re-hospitalization for any CV cause; All-cause mortality

**D.4.9. Sample size justification:** The end of study CIMT value will be subtracted from the baseline CIMT value and divided by the length of follow-up. The rate of change in CIMT (mm/yr) between treatment arms will be tested with a two sided t-test. The rate of change in common CIMT in treated patients is around 0.085 mm/yr with a standard deviation of 0.035. We assume that polypill improvement leads to a halting of CIMT progression with an assumed rate of change of 0.0825 mm/yr. With a two sided alpha of 0.05 and a 90% power we need 82 patients (104 patients with 20% drop-out rate).

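### Table 1 dates no outcome at months 3, 6 or 9, and systolic BP is compared only as change to month 12, so about 24 of 120 patients would lack the value that comparison needs

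*Combined protocol and SAP*

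**What the plan says.** Section D.4.7.3 sets "scheduled visits at months 1, 3, 6, 9 and 12 for clinical assessments and primary, secondary and tertiary/feasibility study outcome evaluations", with Table 1 given as the reference for what is evaluated. The timings stated in the plan are:

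- **CIMT (primary), D.4.7.5:** "Carotid Doppler ultrasonic evaluation at baseline and month 12".
- **Adherence, Table 1:** "This will be measured at baseline and at month 12 clinic visits".
- **Quality of life, treatment satisfaction, cognition, depression, Table 1:** baseline (month 0) and month 12.
- **Creatinine/eGFR, Table 1:** "formula at baseline and months 1 and 12". This is the only row with a post-baseline date before month 12.
- **Systolic BP, Table 1 (tertiary/feasibility):** "Mean change in SBP at month 12 from baseline will be compared in the two treatment groups". LDL cholesterol is treated the same way.
- **No date in Table 1:** liver enzymes, side effects ("Adverse events will be closely monitored & side effects will be documented"), discontinuations, regimen adjustments, modified Rankin score, the BP-control definition and clinical events.

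B.3 gives BP a planning role: the trial is to "collect preliminary data on blood pressure and lipid control and cardiovascular events", and risk-factor control estimates are among the results meant to inform later studies even if the primary endpoint is missed. D.4.9 allows for drop-out ("104 patients with 20% drop-out rate"), and D.4.5 sets the number randomised at 120. D.4.10 plans linear regression for continuous outcomes with data-driven covariate selection, Cox models for events, and multiple imputation and propensity score methods for missing data. It does not name baseline systolic BP as a covariate for the BP comparison.

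**The concern.** Patients in both arms attend five times after baseline, yet the plan assigns no outcome to three of those visits and does not describe their clinical assessments. Site staff cannot tell from it what to record for research purposes at months 3, 6 and 9.

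BP is where this matters most. Three of the five polypill components are antihypertensives, and the BP effect is wanted for the phase 3 design. The stated comparison takes one post-baseline visit and subtracts baseline. A change score is less precise than baseline adjustment, and a patient missing at month 12 contributes nothing to the comparison unless a value is imputed. An on-treatment BP reading would be an obvious predictor for such imputation, but the plan does not say that one will be in the dataset. Interim readings that were never recorded cannot be recovered later.

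**Working it through.** **Inputs from the plan.** 120 randomised (D.4.5); 20% drop-out (D.4.9); visits at months 1, 3, 6, 9 and 12 (D.4.7.3).

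**Assumptions.** The documents give no BP standard deviation or correlation. I assume equal variances and one correlation r between any two visits, baseline included, with r from 0.4 to 0.7. Results are relative, so no standard deviation is needed.

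**Step 1: the drop-out allowance.** The plan needs 82 patients, 41 per arm. 41/0.8 = 51.25, rounded up to 52 per arm, or 104, which matches D.4.9. The 82 concerns CIMT and is not used below.

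**Step 2: missing month-12 values.** 120 × 0.20 = 24 patients without month-12 systolic BP and 96 with it. The standard error is √(120/96) = 1.12 times that with all 120.

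**Step 3: change score against baseline adjustment at month 12.** Variance is proportional to 2(1 − r) for the change score and 1 − r² after adjustment, so the ratio is (1 + r)/2.

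| r | Change score | Adjusted | Variance ratio | SE reduction |
|---|---|---|---|---|
| 0.4 | 1.20 | 0.84 | 0.70 | 16% |
| 0.5 | 1.00 | 0.75 | 0.75 | 13% |
| 0.7 | 0.60 | 0.51 | 0.85 | 8% |

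**Step 4: what interim visits add to the month-12 difference.** Given baseline, the correlation between two visits is c = r/(1 + r). Let R²ₖ = kc²/(1 + (k − 1)c) be the share of month-12 variance explained by k interim visits. Among completers alone, interim visits add no precision at month 12; the gain comes from drop-outs.

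- Upper case, all 24 drop-outs seen at months 1, 3, 6 and 9: variance ratio = 1 − R²₄ × 24/120. For r = 0.4, R²₄ = 0.176 and the ratio is 0.965 (SE down 1.8%). For r = 0.7, R²₄ = 0.303 and the ratio is 0.939 (SE down 3.1%).
- Drop-out uniform over the year: 22, 18, 12 and 6 of the 24 are seen at months 1, 3, 6 and 9, so n₁ to n₄ are 118, 114, 108 and 102. Variance ratio = (1 − R²₄) + Σ(R²ₖ − R²ₖ₋₁) × 96/nₖ, with R²₀ = 0. This gives 0.973 for r = 0.4 (SE down 1.3%) and 0.951 for r = 0.7 (SE down 2.5%).

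**Step 5: average over months 3, 6, 9 and 12, completers, baseline-adjusted.** Variance is proportional to (1 + 3r)/4 − r², against 1 − r² for month 12 alone.

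| r | Months 3-12 mean | Month 12 alone | Variance ratio | SE reduction |
|---|---|---|---|---|
| 0.4 | 0.390 | 0.84 | 0.464 | 32% |
| 0.5 | 0.375 | 0.75 | 0.500 | 29% |
| 0.7 | 0.285 | 0.51 | 0.559 | 25% |

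Step 5 concerns average BP over the period, so its gain cannot be credited to the month-12 difference.

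**The case against.** The best defence is that Table 1 is a table of definitions, not a schedule. D.4.7.3 can be read as evaluating each outcome at the times Table 1 gives, with the undated rows covered at the interim visits. Systolic BP is tertiary/feasibility, the primary CIMT outcome is unaffected, and change at month 12 is a legitimate target for a 12-month pilot. All of this stands. It makes the visit sentence an incomplete specification rather than a flat contradiction, and it limits the weight of the point.

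A reader might go further in four ways that the documents do not support.

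- *Drop-outs leave no post-baseline data.* Month-1 creatinine, adverse events, discontinuations and follow-up time in the Cox models remain available.
- *BP is not measured between baseline and month 12.* It may be taken at the interim clinical assessments. The plan only fails to say so and gives such readings no analytic use.
- *Imputation would rest on baseline data alone, and the BP difference would be biased.* D.4.10 specifies no imputation model, and on-study variables could enter it. Stopping treatment is not the same as leaving follow-up, section E plans home visits and transport stipends to limit loss, and nothing shows differential drop-out.
- *Interim visits would shrink the month-12 standard error by a quarter or more.* Step 4 gives 1-3%.

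D.4.10 could also bring baseline BP into a regression through covariate selection, in which case part of the Step 3 gain would already be realised. The plan does not commit to that.

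**Conclusion.** The point holds as a gap in specification with a modest statistical cost. Table 1 assigns nothing to months 3, 6 or 9, and the stated systolic BP comparison uses month 12 minus baseline only. About 24 of 120 patients would lack the value for it if the plan's 20% drop-out occurs. The largest gain for the month-12 estimate comes from baseline adjustment (standard error down about 8-16%). Interim visits add about 1-3% and let early leavers contribute under missing-at-random. The 25-32% reduction applies only to the months 3-12 average among completers. These percentages rest on the equal-correlation assumption, with r from 0.4 to 0.7. The change is worth making because the plan relies on the BP estimate to design phase 3 and the visits already take place; the primary analysis does not depend on it.

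**What to change.** 1. In Table 1, date systolic and diastolic BP at baseline and months 1, 3, 6, 9 and 12 in both arms, using the average of three readings each time. D.4.6 specifies such an average for baseline systolic BP only, so its extension to later visits and to diastolic BP must be written in.
2. In D.4.10, replace the change-score comparison of systolic BP with one baseline-adjusted repeated-measures model using all visits.
3. Report the month-12 difference from that model and, labelled as a separate estimand, the mean difference over months 3-12. State the missing-at-random assumption.
4. Give the timing of the undated Table 1 rows, so that D.4.7.3 points to a usable schedule of assessments.

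The cost is three cuff readings at visits already planned, a little more data entry, one more reported BP estimate, and short edits to Table 1 and D.4.10. No visit is added and no treatment changes.

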#### D.4.8. Outcome measures:

**Table 1.** Definitions of Primary & Secondary Outcome Measures to be assessed in SMAART Trial.

Variable	Brief Description
Carotid Intimal Media Thickness Primary Outcome Measure	End of study CIMT value will be subtracted from baseline CIMT value & divided by length of follow-up & the rate of change in CIMT (mm/yr) between treatment arms & change in intima-media (artery wall) thickness and extent of atherosclerotic plaques in the carotid artery bifurcation measured.
Change in Adherence to therapy Secondary outcome measure	This will be measured at baseline and at month 12 clinic visits using the self-reported Morisky-Green questionnaire(MAQ)  and pill count. Patients have to meet both criteria for adherence at the in-person visits to be considered adherent.
Safety & Tolerability Indicators Secondary outcome measure	Renal function: Serum creatinine measurements to calculate eGFR using the CKD-EPI  formula at baseline and months 1 and 12. Liver function: Elevations in liver enzymes will be assessed, if AST or ALT rises >5x Side effects profile: Adverse events will be closely monitored & side effects will be documented according to the NIH/NCI Common Toxicity Criteria  Discontinuation of medications: Reasons and clinical indications for stopping treatment in both arms will be compared in both arms. Regimen adjustments: Reasons for modifications in dosages including addition of new CVD agents, will be assessed in both treatment arms.
Health-related Quality of Life	The EQ-5D questionnaire  will be used to assess state of health of study subjects at baseline and Month 12.
Change in Patient Satisfaction	The treatment Satisfaction Questionnaire  for Medication will be administered at baseline and month 12.
Cognitive Dysfunction Indices	The Montreal Cognitive Assessment (MOCA) scale  will be used to assess global cognitive dysfunction at months 0 and 12.
Functional Status	Functional status after stroke will be assessed using the modified Rankin scale with a score from 0 to 6.
Depression	Depression will be assessed using the Beck Depression Inventory and Hamilton Rating Scale for Depression at months 0 and 12. 

CVD Risk Factor Control Tertiary/feasibility	1. Blood pressure control will be defined as Systolic BP <140 mmHg and/or diastolic DP <90mmHg or (>135/85mmHg in diabetes patients). Mean change in SBP at month 12 from baseline will be compared in the two treatment groups. 2. Dyslipidemia: control will be defined by change in mean LDL-cholesterol <100mg/dl or <70mg/dl. Mean change in LDL-C at month 12 from baseline will be compared in the two treatment groups.
Incidence of Adverse events Tertiary/feasibility	1. Recurrent stroke: fatal/ severely disabling stroke or non-fatal stroke; Coronary Artery Disease: Acute STEMI/NSTE deaths 2. Re-hospitalization for any CV cause; All-cause mortality

**D.4.9. Sample size justification:** The end of study CIMT value will be subtracted from the baseline CIMT value and divided by the length of follow-up. The rate of change in CIMT (mm/yr) between treatment arms will be tested with a two sided t-test. The rate of change in common CIMT in treated patients is around 0.085 mm/yr with a standard deviation of 0.035. We assume that polypill improvement leads to a halting of CIMT progression with an assumed rate of change of 0.0825 mm/yr. With a two sided alpha of 0.05 and a 90% power we need 82 patients (104 patients with 20% drop-out rate).

**D.4.10. Statistical analysis plan:** Prior to addressing each hypothesis, univariate descriptive statistics and frequency distributions will be calculated as appropriate for all biological variables (including gender, age) comparing individuals by treatment arms (Polypill arm vs usual care arm). Briefly, box plots will be used to examine the relative distribution of variables stratified by treatment arm. Non-parametric and equivalent parametric statistics will be utilized to compare groups. Appropriate regression models (linear regression for continuous outcomes such as carotid-media thickness; Cox-proportional hazards regression for time to event measures such as recurrent strokes, CVD events, deaths and defaults) will be used to estimate the association of covariates with each outcome. When building models for each specific aim, the first stage of the model building algorithm will involve testing if the individual covariates are correlated with the main outcome variables. A liberal alpha=0.20 will be used for these unadjusted analyses. Once the initial pool of candidate predictors has been identified, regression models consisting of multiple covariates will be fitted to identify potential confounders and effect modifiers. To achieve unbiased and robust results, optimal combinations of predictors, including interaction effects, will be identified and used for further analysis based upon whether or not they are a confounder, by whether they did not improve the model fit, or increased the standard error of the parameter estimate of the primary covariates. Finally, each model will be rigorously assessed for collinearity and goodness of fit using residual analysis. Model diagnostics will be performed using tools (in SAS or STATA) that detect outliers and influential data points. We will use diagnostic measures such as residual deviance, the hat matrix diagonal and residual chi-squared deviance and the difference between chi-square goodness-of-fit when an observation is deleted. Plots of these against predicted values will be used to investigate the influence of each data point on the model. We will handle missing data using several techniques including multiple imputation and propensity score methods.

**D.4.11. Data Safety Monitoring Board (DSMB):** A DSMB comprised of three experienced external experts will meet twice per year to review the safety, ethics, and outcomes of the study.

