**B.2. Significance:** Current projections are that the already overwhelming burden of strokes and other cardiovascular diseases (CVDs) in Africa and other LMICs will continue to escalate over the coming decades as known vascular risk factors such as hypertension, dyslipidemia, obesity and diabetes burgeon in these populations due to adoption of western lifestyles, lack of awareness of the association between vascular risk factors and CVD occurrence and poor primary healthcare infrastructure for the control of non-communicable diseases. The notion that >90% of strokes can be prevented through risk factor modification is an important impetus to understand context specific and relevant risk factors for stroke in SSA in order to stem the rising tide of stroke. The FOA for this R21 funding mechanism cites "*the development of innovative, collaborative research projects on brain and other nervous system..., relevant to low-and middle-income countries*" and also "*lack of adequate prevention and treatment in LMICs is a major contributor to the burden of disease and disability*". Identifying strategies to reduce vascular risk in LMIC could meet a global goal of reducing chronic disease death rates by an additional 2% per year, with only a moderate rise in health expenditure. Thus the overarching objective of the Stroke Minimization through Additive Anti-atherosclerotic Agents in Routine Treatment (SMAART) trial in response to the NIH FOA (PAR-11-031) is to assess in a phase 2 pilot/pragmatic RCT, whether a polypill containing fixed doses of 3 antihypertensives, a statin and antiplatelet therapy taken once daily orally would result in carotid intimal thickness regression-a surrogate marker of atherosclerosis, improved adherence and tolerability compared with 'usual care' group on separate, individual secondary preventive medications among Ghanaian stroke survivors in a single center study. A 12-month follow up is planned to allow sufficient time to assess sustainability of adherence to the polypill, overcome the time-lag effect required for translation of the CVD prevention benefits of SBP and LDL-C control and initiate the collection of 'hard cardiovascular outcome measures' such as recurrent strokes and vascular events to inform the design of a larger future phase 3 SMAART trial to assess these clinical outcomes in a multi-center study. SMAART will also incorporate building of institutional and human research capacity for the conduct of interventional studies centered around evaluating outcomes of stroke. It is notable that SMAART involves several early stage SSA investigators ([name], [name], [name]), which is key for building sustainable human capital and clinical trial research capacity in SSA. Findings from the SMAART study will undoubtedly contribute meaningful data from the African perspective towards the formulation of guidelines for global adoption of polypills into routine care for secondary CVD risk prevention by international bodies such as the World Health Organization. In the long-term, findings from SMAART could serve as a scalable strategy for managing CVD risk among stroke survivors in SSA, and even other LMICs.

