#### **D.4. SMAART (Specific Aims 1 and 2):**

- To evaluate whether a polypill-based treatment strategy vs. usual care will result in carotid intimal media thickness stabilization/regression among recent stroke patients at one year after an index ischemic stroke. (Aim 1)
- To evaluate whether a polypill-based treatment strategy vs. usual care will improve vascular risk reduction drug adherence and tolerability among recent stroke patients at one year after an index ischemic stroke. (Aim 2)

**D.4.1. Study Design:** SMAART is a phase II randomized, open label, blinded endpoint clinical trial to evaluate the effect of a polypill taken once daily orally in improving CMIT regression and adherence to secondary risk reduction drug intake vs. 'usual care' group with separate individual secondary preventive medications among Ghanaians with recent onset stroke/TIA in a single center study.

**D.4.2. Participants:** The participants will include 120 adult Ghanaian recent stroke/TIA patients (within two months of stroke onset) meeting inclusion/exclusion criteria who will be randomly assigned to either intervention or usual care arms.

**D.4.3. Inclusion Criteria:** 1. Above the age of 18 years; male or female; 2. Stroke/TIA diagnosis no greater than two months before enrollment. Ischemic strokes including lacunar, large-vessel atherosclerotic, cardio-embolic subtypes are eligible 3. Subjects with stroke may present with at least one of the following additional conditions: Documented diabetes mellitus or previous treatment with oral hypoglycemic or insulin; documented hypertension >140/90mmHg or previous treatment with anti-hypertensive medications; Mild to moderate renal dysfunction (eGFR 60-30ml/min/1.73m^2); Prior myocardial infarction 4. Legally competent to sign informed consent.

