**D.4.4. Exclusion criteria:** 1. Unable to sign informed consent, 2. Contraindications to any of the components of the polypill, 3. Hemorrhagic stroke, 4. Severe cognitive impairment/dementia or severe global disability limiting the capacity of self-care, 5. Severe congestive cardiac failure (NYHA III-IV), 6. Severe renal disease, eGFR <30ml/min/1.73m^2), renal dialysis; awaiting renal transplant or transplant recipient, 7. Cancer diagnosis or treatment in past 2 years, 8. Need for oral anticoagulation at the time of randomization or planned in the future months, 9. Significant arrhythmias (including unresolved ventricular arrhythmias or atrial fibrillation) 10. Nursing/pregnant mothers, 11. Do not agree to the filing, forwarding and use of his/her pseudonymized data.

**D.4.5. Recruitment of study subjects:** A total number of 120 patients will be randomized (1:1) to treatment arms. Patients with stroke meeting inclusion/exclusion criteria will be recruited from the Family Medicine, Internal Medicine and Neurology outpatient clinics at KATH. Randomization will take place within 8 weeks of the index event (ischemic stroke) in a 1:1 ratio to one of the two arms: Polypill versus Usual care.

**D.4.6. Randomization Procedure:** Randomization of subjects in blocks of four will be conducted by a statistician ([name] PI) using a computer-generated random sequence of numbers. Consented participants will be assigned to either study arm at the baseline visit using the computer generated randomization sequence. The randomization sequence uses a minimization algorithm to ensure balance of prognostic factors such as stroke severity, average of 3 recorded baseline systolic BP measurements, & whether or not they are on background BP lowering agents, lipid modifiers & antithrombotic agents. Each sequence generated will be kept concealed in an envelope which will be opened by the Research Coordinator in the presence of the consenting study participant at enrollment.

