**D.4.7. Study protocol:** The diagnosis of stroke will be defined as an acute episode of focal cerebral, spinal or retinal dysfunction caused by infarction of central nervous system tissue, not resulting in death. Patients meeting eligibility criteria will be allocated to the experimental or active comparator arm. Patients allocated to the experimental arm will receive Two (2) (Polycap ®) taken orally once a day. Patients allocated to the usual care arm will receive standard of care therapies for secondary prevention with drugs and doses left at the discretion of the treating physicians. Patients assigned to Polypill will have their antihypertensive agents, lipid modifiers and anti-thrombotic agents withdrawn & replaced with the Polypill if they are already receiving such treatments before enrollment. Since our focus is to *isolate the effect of the polypill strategy itself & create equipoise*, at study inception providers for patients in both study arms will receive a brief one-time (Skype-based) training & a one time email synopsis on guideline recommended biomarker targets after stroke.

**D.4.7.1. Screening/run-in period-4 weeks:** All potentially eligible participants referred to or who contact the study team directly will undergo screening to determine eligibility using the pre-specified criteria (see Human Subject Protection document).

**D.4.7.2. Enrollment evaluation:** Information on stroke type from a cranial CT scan performed within 10 days of stroke symptom onset will be reviewed by the MPI ([name]), stroke subtype information where available will be sought to classify ischemic stroke using the TOAST classification into cardio-embolic, large-artery and lacunar ischemic stroke. Stroke severity and functional status at enrollment will be assessed using the modified NIHSS and Modified Rankin Score, followed by a detailed assessment of vascular risk factors namely hypertension, diabetes mellitus, dyslipidemia, cigarette smoking, cardiac diseases (atrial fibrillation, ischemic heart diseases, cardiomyopathies), from history and physical examination. Blood samples for baseline assessments of renal and liver function tests, lipid profile and HbA1C will be collected and contraindications for study medications assessed. All concomitant medications will be recorded in the case report form.

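### The Aim 2 adherence outcome is titled a change but defined as a yes/no status at baseline and month 12 only: the analysis should be fixed as baseline-adjusted month-12 status, and the existing interim visits used to show the time course

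*Combined protocol and SAP*

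**What the plan says.** In the combined protocol and SAP, Aim 2 (section D.4) asks whether the polypill strategy, against usual care, "will improve vascular risk reduction drug adherence and tolerability among recent stroke patients at one year after an index ischemic stroke".

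The matching row of Table 1 (section D.4.8) carries a title that speaks of change. Its text sets two measurement times and two instruments: "This will be measured at baseline and at month 12 clinic visits using the self-reported Morisky-Green questionnaire(MAQ", plus pill count. It then sets the scale: "Patients have to meet both criteria for adherence at the in-person visits to be considered adherent". It gives no formula for a change.

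Entry without preventive drugs is foreseen. Section D.4.6 minimizes on "whether or not they are on background BP lowering agents, lipid modifiers & antithrombotic agents", and section D.4.7 replaces a polypill patient's drugs "if they are already receiving such treatments before enrollment". Neither section says how baseline adherence is scored when there is no drug to count.

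Section B.2 explains the 12-month follow-up partly as a way "to allow sufficient time to assess sustainability of adherence to the polypill", and section B.3 repeats that purpose. Section D.4.7.3 provides "scheduled visits at months 1, 3, 6, 9 and 12 for clinical assessments".

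The analysis plan (section D.4.10) gives examples of models for continuous and time-to-event outcomes, chooses covariates through a screen at alpha 0.20, and names multiple imputation among its methods for missing data.

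**The concern.** The title and the definition point to different analyses. A change between two yes/no values takes the values -1, 0 or +1. It needs a baseline value for everyone, and a patient on no preventive drugs has no pills to count. For a polypill patient who was already treated, the baseline value also refers to a regimen that the trial then withdraws. Month-12 status has neither difficulty, and it matches the wording of Aim 2. Because covariates are picked by a screen, the plan does not guarantee that baseline adherence will be used as an adjustment variable, although it is collected.

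The second issue is the time course. With one post-baseline value, the pilot can report who is adherent at one year. It cannot report whether adherence held or fell, or when. A patient who misses month 12 contributes no follow-up adherence value, so multiple imputation would have only baseline adherence to work from. What is not collected at the interim visits cannot be recovered afterwards, and a main purpose of this pilot is to inform a larger trial.

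**Working it through.** The documents give no adherence rate, effect size or power for this outcome, so there is no stated figure to reproduce. The calculation below is an illustration of scale.

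**Inputs**
- Baseline and usual-care month-12 adherence: 57%, taken as 100% minus the 43% non-adherence in section B.1.5.
- Polypill month-12 adherence: 77%. This is an assumption and is not in the documents.
- Patients per arm: 120 randomized less 20% drop-out (the rate in section D.4.9) = 96, or 48 per arm.
- Untreated at entry: none, in the main illustration.
- Correlation r between the continuous tendencies underlying baseline and month-12 adherence: 0.3 to 0.9, assumed.

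**Formulas.** Let p0 be baseline adherence, p month-12 adherence in an arm, and c the covariance of the two yes/no values in that arm, that is, P(adherent at both) − p0·p from a bivariate normal model. The variance per patient is:
- change score: p0(1−p0) + p(1−p) − 2c
- month-12 status, unadjusted: p(1−p)
- month-12 status, adjusted with a common slope b: p(1−p) + b²·p0(1−p0) − 2bc, with b = (mean of c over the arms)/[p0(1−p0)]

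The SE of the contrast is the square root of (sum of the two arm variances)/48. Power = Φ(0.20/SE − 1.96).

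**Worked case, r = 0.7**
- p0(1−p0) = 0.57 × 0.43 = 0.2451, and 0.77 × 0.23 = 0.1771.
- c = 0.4455 − 0.3249 = 0.1206 (usual care); c = 0.5306 − 0.4389 = 0.0917 (polypill).
- Change: (0.2451 + 0.2451 − 0.2412) + (0.2451 + 0.1771 − 0.1834) = 0.488; SE = √(0.488/48) = 0.101; power 51%.
- Unadjusted: 0.2451 + 0.1771 = 0.4222; SE = √(0.4222/48) = 0.094; power 57%.
- Adjusted: b = 0.433; variances 0.1866 + 0.1437 = 0.3303; SE = √(0.3303/48) = 0.083; power 67%.

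**All settings, nobody untreated (SE, power)**

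| r | Change score | Month 12, unadjusted | Month 12, adjusted |
|---|---|---|---|
| 0.3 | 0.125, 36% | 0.094, 57% | 0.092, 58% |
| 0.5 | 0.114, 42% | 0.094, 57% | 0.089, 61% |
| 0.7 | 0.101, 51% | 0.094, 57% | 0.083, 67% |
| 0.9 | 0.081, 69% | 0.094, 57% | 0.071, 80% |

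The adjusted analysis is the most precise in every row. The change score is worse than unadjusted status up to r = 0.7 but better at 0.9.

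**Bias.** In 20,000 simulated trials per setting, the mean contrast was 0.199 to 0.201 for all three analyses against a true 0.20.

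**Untreated share.** Section C.3 reports, one year after stroke, 30% without a statin and 35% without an antithrombotic. If that held at entry, the share on no drug at all could be at most min(30%, 35%) = 30%, and it could be near 0. Suppose 20% are untreated, scored as non-adherent at baseline in the change score and given their own category in the adjusted analysis. The SEs are then 0.128 versus 0.092 (r = 0.3), 0.110 versus 0.085 (0.7) and 0.096 versus 0.076 (0.9). The 20% is an assumption without a source in the documents.

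**Time course.** At 20% drop-out, 0.20 × 120 = 24 patients would have no post-baseline adherence value. For one arm at one visit, the 95% half-width is 1.96 × √(0.57 × 0.43/48) = 14 points, or 1.96 × √(0.77 × 0.23/48) = 12 points.

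**The case against.** Only the row title implies a change score. The row text defines a status, and Aim 2 is framed at one year. The blood pressure and LDL rows state outright that mean changes will be compared, whereas the adherence row does not. A plain month-12 comparison is therefore a natural reading, and it needs no baseline value. This stands. Against that comparator, adjustment raises power from 57% to between 58% and 67% at correlations of 0.3 to 0.7, a gain of 1 to 10 points. The correlation may also be low on polypill, because the earlier drugs are replaced. With 0.7 in usual care and 0.1 to 0.3 on polypill, adjusted power is 61% to 62%.

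A reader might infer that month 12 says nothing about sustainability. That goes too far, since being adherent at one year is part of the answer. What is missing is the trajectory. "Reasons and clinical indications for stopping treatment in both arms will be compared in both arms" (Table 1), and section D.4.10 lists time to defaults, but defaults are not defined and stopping treatment is not the two-criteria measure. These cover the gap only in part.

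It can also be said that section D.4.7.3 has secondary outcomes evaluated at every visit. It defers to Table 1, however, and the adherence row names only baseline and month 12, while the renal-function row in the same table adds month 1.

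A reader might infer that the plan rules out a model for yes/no outcomes. It does not: its models are given as examples, and several of its diagnostics suit logistic regression. Section E also plans home visits and transport stipends, which may keep missing data below 20%.

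**Conclusion.** The point holds in a limited form. Title and definition disagree. A change is undefined for patients who enter on no drugs, and a change score is less precise than baseline-adjusted month-12 status in every setting examined. The gain from the fix is large only if a change score was intended or the correlation is high. The sizes rest on an assumed 77% polypill rate, assumed correlations and an unknown untreated share.

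A reader might infer that the randomized comparison is biased. It is not, under either reading. The cost is in precision, in interpretation and in a time course that falls short of the purpose stated in sections B.2 and B.3. For a secondary outcome in a pilot, the importance is minor to moderate.

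**What to change.** (a) Define the Aim 2 outcome as the between-arm difference in adherence status at month 12, in place of a change from baseline. Pre-specify adjustment for baseline adherence in three categories: adherent, not adherent, on no drugs. This costs only wording, because the baseline value is already collected.

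(b) Give the MAQ at the scheduled visits at months 1, 3, 6 and 9 in both arms. Report MAQ-defined adherence over months 1 to 12 by arm as a separate descriptive analysis, using the MAQ component alone at every visit, including month 12, so that it is never mixed with the two-criteria composite. Use the interim MAQ values as auxiliary variables in the planned multiple imputation. The cost is a short questionnaire at four existing visits and the data entry. Repeated questioning may itself affect adherence. With half-widths of 12 to 14 points, the time course will be descriptive only.

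For clarification only: state the MAQ and pill-count cut-offs and the model for the yes/no outcome.
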